Among the women enrolled in the translational sub-study at Yale, the following secondary outcomes will be explored:

- Plasma proteomic profiles (measured by mass spectrometry) after 2 hours of treatment comparing patients receiving IV oxytocin and nipple stimulation. Plasma samples from patients who have not undergone cervical ripening will be collected as additional control to account for differences achieved from cervical ripening alone. Plasma samples from patients in early spontaneous labor will be obtained to compare how closely nipple stimulation therapy and IV oxytocin approximate the molecular phenotype of spontaneous labor.
- Changes in plasma proteomic profiles from baseline (prior to treatment), 2 hours, and the time of adequate contractions in each treatment group
- Plasma micro-RNA profiles (measured by bulk RNA sequencing) after 2 hours of treatment among patients receiving IV oxytocin, nipple stimulation, and patients in early spontaneous labor.
- Changes in plasma micro-RNA profiles from baseline (prior to treatment), 2 hours, and the time of adequate contractions in each treatment group
- Urine prostaglandin profiles (measured by mass spectrometry) at 2 hours comparing patients receiving IV oxytocin, nipple stimulation, nipple stimulation who cross-over to IV oxytocin, un-ripened control patients, and patients in spontaneous labor.
- Changes in urine prostaglandin profiles from baseline (prior to treatment), 2 hours, and the time of adequate contractions in each treatment group

Among the women enrolled in the translational sub-study for milk collection, the following secondary outcomes will be explored:

- Changes in milk sodium and conductivity levels from before delivery (in the nipple stimulation therapy group only), and 12, 24, 48 hours after delivery. For mothers hospitalized for a longer period, additional samples at 72 hours will be collected or later up to twice a day.
- Milk macronutrient composition at 48 hours after delivery in each treatment group.
- Milk RNA profile at 48 hours after delivery in each treatment group.

The following secondary neonatal outcomes will be explored:

- Intrapartum fetal death or neonatal death (assessed until birth hospitalization discharge or death)
- Neonatal Apgar score ≤ 3 at 5 minutes of life
- Umbilical cord arterial pH < 7.0 or base excess > 12 mmol/L; or umbilical cord venous pH < 7.0 or base excess > 12 mmol/L if arterial blood sample not available

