For collection of plasma and urine from patient participants in early spontaneous labor (defined as <6 cm dilated with intact membranes), inclusion criteria will be:

- Age 18 years and older
- Nulliparous

- Gestational age 36 0/7 and greater
- Singleton gestation
- Ability to give informed consent
- Presenting in early spontaneous labor defined as <6cm dilated with intact membranes.
- Patient and primary obstetric provider intend for patient to continue spontaneous labor

For collection of plasma and urine from patient participants in early spontaneous labor (defined as <6 cm dilated with intact membranes), exclusion criteria will be:

- Patient has performed nipple stimulation in the preceding 24 hours, received outpatient prostaglandin therapy, or had “membrane stripping” in the preceding 24 hours
- Patient is expected to have labor complications preventing continued spontaneous labor, such as arrest of dilation or fetal intolerance of labor

6 - Methods

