6.1.3 Concomitant therapy

There are no restrictions on use of concomitant medications. However, for those who are randomized to nipple stimulation, the use of exogenous oxytocin intravenous solution will not be permitted until at least two hours of nipple stimulation alone has been attempted, unless this is decided by the treating obstetric provider. Stimulation may be discontinued at any time that the treating obstetric provider decides. If there are any signs of fetal heart rate abnormalities on the cardiotocography, the obstetric provider should provide usual care measures such as discontinuation of stimulation, lateral positioning, intravenous hydration, etc. Initiation of exogenous oxytocin intravenous solution prior to two hours of nipple stimulation alone will be considered a cross-over.

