The use of amniotomy (if the subject has intact membranes) and other labor procedures will be at the discretion of each subject's responsible maternity care provider (pragmatic study) and considered standard of care. If standard of care is altered based on clinical decision making by the subject's responsible treating physician or midwife, the subject will still remain in the study as long as the subject does not withdraw her consent to continue in the study.

5. Subject Management and Follow-Up

All subjects will be monitored for progression of labor and their fetus' response to labor by their responsible treating obstetrician or midwife. Each subject will undergo individualized assessment by their treating obstetrician or midwife, and the clinical decision will be made by the treating obstetrician or midwife if or when subjects in the nipple stimulation arm will be switched to the standard of care with exogenous oxytocin administration. There can be no absolute cut-offs for time or contraction responses since standard of care dictates individualized assessments for labor progression and fetal response; each birth experience is unique. Subjects in both arms of the trial should be allowed adequate time to labor before considering the induction "failed" and proceeding to cesarean section. An induction will be considered "failed" after at least 24 hours of exogenous oxytocin administration has failed to generate regular (e.g., every 3 minutes) contractions and cervical change, as is considered standard of care (36). Additionally, exogenous oxytocin generally should be administered for at least 12 hours after membrane rupture before considering the induction to have failed as is considered standard of care. (37). The time devoted to cervical ripening and/or nipple stimulation will not be included when calculating the length of induction for diagnosing failed induction.

It is expected that the fetal heart rate and uterine activity will be monitored continuously during labor and that subjects will stay in the hospital until delivery once the induction is started as is considered standard of care. Aside from the interventions described above, labor and delivery management decisions will be left to the discretion of the subject's responsible maternity care provider as is considered standard of care.

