Specimen collection will be conducted as described in the previously published methodology (38).

For patients in non-spontaneous labor, blood and urine will be collected at 1) prior to cervical ripening, 2) after cervical ripening, and 3) after 2 hours of treatment (IV oxytocin or nipple stimulation). This is a maximum of 3 blood samples per subject. For control patients in spontaneous labor, a blood and urine specimen will be obtained at enrollment. Blood may be drawn in several ways depending on what is clinically appropriate: (1) venipuncture; (2) IV catheter placed as part of standard of care (SOC); and/or (3) IV catheter placed for research purposes. The research IV may be placed in addition to the SOC IV and may be used instead of research venipuncture. That is, research venipuncture and research IV will not both occur at the same time (only one or the other).

Urine samples (amount variable by patient) will be collected mid-stream in a sterile screw-top container 1) prior to cervical ripening, 2) after cervical ripening, and 3) after 2 hours of treatment (IV oxytocin or nipple stimulation). If a patient has an indwelling foley catheter, urine from the tubing will be collected at the time of adequate contractions. If a patient is being intermittently catheterized for urine, a urine sample will be collected as able, but the patient will not undergo additional bladder catheterization for the purpose of this study.

Blood and urine samples may not be collected at one or more of the specified time points due to logistical issues (eg. patient enrolled after cervical ripening, labor floor acuity prevents nurse from drawing blood, patient delivers before time point, etc.) and/or clinical care taking precedence.

Proteomic profiling will be conducted by mass spectrometry at the Keck MS & Proteomics Resource. Prostaglandin measurements will be performed by an external core facility with expertise in prostaglandin mass spectrometry methods (Vanderbilt Eicosanoid Facility). microRNA profiling will be conducted via bulk RNA sequencing by the Yale Center for Genome Analysis/Keck Core.

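### In the exploratory urine prostaglandin comparison of induced women with spontaneous-labor controls, a prostaglandin given for ripening is left open in one group and its outpatient use is excluded from the other

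*Protocol*

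**What the plan says.** **The comparison.** Protocol 5.2.2 lists, for the Yale sub-study, "Urine prostaglandin profiles (measured by mass spectrometry) at 2 hours comparing patients receiving IV oxytocin, nipple stimulation". The same item goes on to "nipple stimulation who cross-over to IV oxytocin, un-ripened control patients, and patients in spontaneous labor". Section 6.4.3.2 makes induction versus spontaneous labor a secondary comparison, and objective 6 in 4.3 names the comparison with early spontaneous labor.

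**Spontaneous-labor controls.** Section 5.3.2 excludes a woman if "Patient has performed nipple stimulation in the preceding 24 hours, received outpatient prostaglandin therapy" applies, or if she had recent membrane stripping. Section 6.2, item 10, also collects receipt of outpatient prostaglandins for these controls. Section 6.3 takes one blood and urine specimen from them, at enrollment.

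**Induced women.** Section 6.1.3 says "There are no restrictions on use of concomitant medications". Under 6.3, "blood and urine will be collected at 1) prior to cervical ripening, 2) after cervical ripening, and 3) after 2 hours of treatment". The baseline data listed in 6.3 include neither ripening method nor agent.

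**Safeguards present.** For plasma, 5.2.2 adds samples from un-ripened patients "as additional control to account for differences achieved from cervical ripening alone". Un-ripened patients are also a urine comparison group; synopsis objective 4 describes them as both un-ripened and unlabored. For adjusted analyses, 6.4.3.2 adds as covariates whatever differences between groups are found.

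**The concern.** The outcome is prostaglandin, and the exposure at issue is a prostaglandin drug. One side of the contrast excludes outpatient use of it and is asked about it. The other side may have received one for ripening, is sampled afterwards, and has no listed field to show who did. If the drug or its metabolites register in the urine measurement, or if ripening changes the body's own production, the induced group's level shifts for a reason unrelated to stimulation, oxytocin or spontaneous onset.

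What is at stake is a secondary, non-randomised reading: how closely each method of induction resembles spontaneous labor in its prostaglandin profile. The trial's primary outcome is not involved.

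**Working it through.** **1. The two groups side by side**

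| | Induced women | Spontaneous-labor controls |
|---|---|---|
| Prior prostaglandin | No restriction (6.1.3) | Outpatient use excluded (5.3.2) |
| Exposure recorded | Not in the baseline list (6.3) | Asked and checked in the chart (6.2) |
| Urine samples | Before ripening, after ripening, after 2 hours of treatment (6.3) | One, at enrollment (6.3) |

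Section 6.3.7 alludes to a further control specimen at active labor. Even if taken, it would not be a pre-labor baseline. No change from an unlabored state can be formed for the controls, so the contrast with them is one of levels.

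**2. Do the safeguards separate drug from labor?**
- Un-ripened, unlabored patients differ from induced women at 2 hours in labor as well as in ripening, so they cannot isolate the drug.
- The samples before and after ripening could show the effect within a woman, but 6.3 accepts that the first may be missing when a woman enrolls after ripening. No stated analysis uses the pair to correct the comparison with controls.
- A covariate cannot separate an exposure that eligibility removes from one group from membership of that group.

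**3. Scale, under assumptions**

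The 6.4.2 table gives for PGE2 an SD of 4.2 ng/mL and a detectable difference of 2.4 ng/mL at 48 per group. Check: (1.96 + 0.84) × 4.2 × √(2/48) = 2.40, so the table's figure reproduces.

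Assume that a share f of induced women is shifted upward by k SD, with 48 induced women against 48 controls and a two-sided 0.05 test (normal approximation). Then, in SD units:
- offset b = f × k
- standard error = √[(2 + f(1 − f)k²)/48]
- with no true difference, chance of significance = 1 − Φ(1.96 − b/SE) + Φ(−1.96 − b/SE)

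For f = 0.5 and k = 1: b = 0.5, SE = √(2.25/48) = 0.2165, b/SE = 2.31.

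| f | k | Offset, SD | Offset × 4.2, ng/mL | Chance of a significant result |
|---|---|---|---|---|
| 0.25 | 0.25 | 0.0625 | 0.26 | 6% |
| 0.5 | 0.5 | 0.25 | 1.05 | 23% |
| 0.5 | 1 | 0.50 | 2.1 | 64% |
| 0.5 | 2 | 1.00 | 4.2 | 98% |

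Masking: suppose the true level is higher in spontaneous labor by 0.572 SD, the difference detectable with 80% power. With f = 0.5 and k = 0.5, the visible difference is 0.572 − 0.25 = 0.322 SD and SE = √(2.0625/48) = 0.207. Power falls to about 34%.

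Both f and k are assumptions. The table shows that either error is possible, not how likely it is.

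**The case against.** **The premise is not documented.** No inpatient ripening agent is named. Misoprostol appears only as an outpatient drug asked about in controls. The provision that "other labor procedures will be at the discretion of each" subject's provider concerns amniotomy and other procedures, not ripening drugs. Nothing says that a ripening prostaglandin would register in the mass-spectrometry measurement, or in which direction. This stands, and it is why no size can be claimed.

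**The exclusion has another purpose.** The same bullet excludes nipple stimulation and membrane stripping, so it serves to define spontaneous onset. A reader might infer that the protocol itself declares prostaglandin exposure a contaminant of the assay. It does not. The asymmetry exists whatever the motive.

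**The randomised comparison.** A reader might infer bias or lost power in stimulation versus oxytocin, because women ripened in different ways are pooled. Ripening before randomisation is balanced in expectation, so there is no bias. The comparison is of change from baseline, supported by ANCOVA on baseline (6.4.3.2), and 5.2.2 defines baseline as before treatment. A stable shift present in both samples cancels; only drift over the 2 hours would remain, and the documents say nothing about it. No power loss should be claimed.

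**This may be settled elsewhere.** The data collection form is an appendix that is not shown, and an analysis plan may exist. Either could cover ripening. But the asymmetry in eligibility and in the listed data is fixed in the protocol, and an analysis plan cannot use an agent that was not recorded without a return to the charts.

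**The un-ripened group may be adequately sized.** The 192 women in 5.3.1 are 4 × 48, which would fit 48 un-ripened patients. That is plausible though not stated, and size does not remove the difference in labor.

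**Conclusion.** The point holds for one contrast: urine prostaglandin levels in induced women against spontaneous-labor controls. Run as written, it can confuse a ripening drug with the way labor began, in either direction. It rests on two conditions that the protocol leaves open: that some induced women are ripened with a prostaglandin, and that this alters the measured urine profile. The documents do not fix the size. The illustrative range of 6% to 98% reflects assumed shares of 25% to 50% and shifts of 0.25 to 2 SD.

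The contrast is secondary, exploratory and not randomised. The trial's primary outcome and the sub-study's randomised change comparison are not biased by it. It is worth correcting because the correction is cheap and the exposure is harder to recover later.

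**What to change.** 1. Record ripening method, agent and time of last dose from the chart for every sub-study woman.
2. Report the urine prostaglandin comparison with spontaneous-labor controls twice: overall, and restricted to induced women without prostaglandin ripening. Show prostaglandin-ripened women separately. Label the comparison exploratory and not randomised.
3. State that baseline for the randomised change comparison is the sample after ripening and before treatment, since 6.3 schedules two samples before treatment.
4. Where both exist, use the samples before and after ripening to describe the ripening effect within women.

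**Cost.** A few chart fields and some analysis wording, with no change to care or sampling. The restricted comparison has fewer induced women. If half were prostaglandin-ripened, 24 of 48 per arm would remain, and the difference detectable against 48 controls would rise from 0.57 SD to 2.80 × √(1/24 + 1/48) = 0.70 SD (2.94 ng/mL for PGE2). Those women are also a clinically selected subset, so the restricted result informs the overall one and does not replace it.

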Secondary and Exploratory Outcome Variables (if applicable) 
The following secondary maternal outcome variables will be explored: operative vaginal delivery, cesarean delivery, time interval from randomization to delivery, postpartum hemorrhage, infection, 3rd or 4th degree perineal lacerations, maternal death, maternal intensive care unit admission.
 
The following secondary patient-centered outcome variables will be explored: labor pain, feelings of control during labor, satisfaction with the birthing process, ability to express and/or collect colostrum and/or breastmilk intrapartum, depression score, and breastfeeding success.
 
The following secondary perinatal outcome variables will be explored: perinatal death, Apgar score <3 at 5 minutes of life, umbilical artery acidemia, neonatal intensive care unit admission, and a composite neonatal severe morbidity measure. In addition, breastfeeding as the sole source of nutrition (BSSN) at the time of delivery hospitalization within the first 72 hours and maximal percent newborn weight loss up to 14 days post-birth will be examined.
 
In the Yale biospecimen sub-cohort, we will measure circulating plasma concentrations of proteins and microRNA and urine metabolites of prostaglandins using unbiased “omics” approaches, comparing patients undergoing induction of labor via intrapartum nipple stimulation versus continuous exogenous oxytocin infusion. The change in these labor biomarkers will also be evaluated in a cohort of patients presenting in early spontaneous labor who will be evaluated as a control.
 
In the milk biospecimen sub-cohort, we will measure milk conductivity and sodium levels to estimate milk maturation (MM) before and after birth. When milk volume allows, we will also measure milk composition (macronutrients) and will use an unbiased approach to study mammary gland function using milk RNA sequencing. We will compare patients

undergoing induction of labor via intrapartum nipple stimulation versus continuous exogenous oxytocin infusion.

Visit Schedule Table (Optional)
--

Study Flow Chart (optional)

Table of Contents

Synopsis	2
Primary Objective	2
Secondary Objectives (if applicable)	2
Study Duration	2
Study Design	2
Study Population	3
Number of Participants	3
Number of Study Sites	3
Primary Outcome Variables	3
Secondary and Exploratory Outcome Variables (if applicable)	3
Visit Schedule Table (Optional)	4
Study Flow Chart (optional)	4
1 – Introduction	8

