5.2.2 Secondary and Exploratory Outcome Variables (if applicable)

The following secondary maternal outcomes will be explored:

- Operative vaginal delivery (defined as delivery with the assistance of forceps or vacuum) and indication
- Cesarean delivery and indication
- Interval from randomization to delivery
- Postpartum hemorrhage (defined as a cumulative blood loss of $\geq 1,000$ mL within 24 hours after the birth process)
- Severe postpartum hemorrhage (defined as any of the following: transfusion; non-elective hysterectomy; use of ≥ 2 uterotonic medications other than oxytocin; other interventions such as uterine compression sutures, uterine artery ligation or embolization, hypogastric artery ligation, balloon tamponade)
- Suspected intraamniotic infection, intrapartum chorioamnionitis, or postpartum endometritis (defined as maternal fever $\geq 38^{\circ}$ Fahrenheit with planned or initiated administration of therapeutic antibiotics) after randomization and prior to delivery hospitalization discharge
- Third- or fourth- degree perineal lacerations
- Lactational mastitis (assessed up to 12 weeks postpartum from breastfeeding survey performed at 4-12 weeks postpartum and medical records)
- Maternal death (assessed until delivery hospitalization discharge)
- Admission to Intensive Care Unit (assessed until delivery hospitalization discharge)
- Subject-reported pain experienced during childbirth using the visual analog scale (28) , measured at 2 hours after start of intervention
- Subject-reported feelings of control during labor using the Labor Agency Scale (29) , assessed during the hospital postpartum stay
- Subject-reported satisfaction with the birthing experience using the validated Birth Satisfaction Scale-Revised (BSS-R) (30) (31), assessed during the hospital postpartum stay
- Subject-reported ability to express and/or collect colostrum and/or breastmilk intrapartum
- Subject-reported perception of milk supply using the validated Perception of Insufficient Milk Supply (PIMS) (40), 2 weeks postpartum

- Subject-reported depression score using the validated Edinburgh Postnatal Depression Scale, assessed (32), 4-12 weeks postpartum
- Subject-reported breastfeeding success using the validated Maternal Breastfeeding Evaluation Scale (MBES) (33), assessed 4-12 weeks postpartum
- Subject-reported breastfeeding success by assessing infant feeding method (breastmilk, formula, or combination) via questionnaire, assessed 6 months postpartum

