6.2 Assessments

Obstetric and perinatal clinical outcomes will be assessed and abstracted through chart review of the electronic medical record of both subjects and their infants by certified trained research members according to the outcome definitions listed in the protocol. Postpartum assessments will be conducted at 2 weeks postpartum and 4-12 weeks postpartum. While the ideal time period is 6-8 weeks postpartum, such a short time-window for follow-up may result in less-than-ideal protocol adherence, and 12 weeks is still within the typically described postpartum period (the “4th trimester”). In addition, economic costs and infant feeding method will be assessed at 6 months postpartum.

To assess patient-centered outcomes, several study questionnaires will be conducted:

1. To assess subject-reported pain experienced during childbirth, the visual analog pain scale (28) will be administered at three different timepoints: (1) prior to initiating study intervention (to obtain baseline); (2) two hours after initiating study intervention; and (3) during postpartum stay prior to delivery hospitalization discharge.
2. To assess subject-reported satisfaction with the childbirth process, the Birth Satisfaction Scale-Revised (BSS-R) (30) (31) will be administered during postpartum stay prior to delivery hospitalization discharge.
3. To assess subject-reported feelings of control during childbirth, the Labor Agency questionnaire (29) will be administered during postpartum stay prior to delivery hospitalization discharge.

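### Section 5.2.2 defines the cord-gas acidemia outcome with the wrong sign on base excess and the maternal infection outcome with fever in the wrong temperature unit

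*Protocol*

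**What the plan says.** Protocol section 5.2.2 lists, among the secondary neonatal outcomes, "Umbilical cord arterial pH < 7.0 or base excess > 12 mmol/L", with a fallback of "umbilical cord venous pH < 7.0 or base excess > 12 mmol/L if arterial blood sample not available". The synopsis names the same outcome "umbilical artery acidemia".

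Among the maternal outcomes in section 5.2.2, infection covers three named intrapartum or postpartum diagnoses. Its defining condition is maternal fever of at least 38 degrees "Fahrenheit with planned or initiated administration of therapeutic antibiotics".

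The synopsis gives the low-Apgar outcome as "Apgar score <3 at 5 minutes of life". Section 5.2.2 sets it at ≤3 "at 5 minutes of life".

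Section 6.2 has clinical outcomes taken from the medical record by "certified trained research members according to the outcome definitions listed in the protocol". Section 6.4.3.3 states that maternal and perinatal morbidity outcomes will be compared between the groups to look for a safety signal. No other part of the protocol corrects any of these definitions.

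**The concern.** Base excess is a signed quantity that falls below zero as metabolic acidosis develops. A threshold of more than +12 is on the wrong side of zero for an outcome called acidemia. A fever threshold of 38 on the Fahrenheit scale lies far below any living patient's temperature, so as a numerical condition it does nothing.

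Both definitions belong to the protocol itself, so this is not detail left to an analysis plan, and a plan that copied them would carry the errors forward. Section 4.1 hypothesises no increase in fetal or neonatal morbidity, and section 6.4.3.3 relies on comparing such outcomes. If the wording were applied as it stands, and equally in both arms, missed acidosis events would shrink the event count and the risk difference. Infection events added for women without fever would pull the risk ratio towards 1. Either effect makes a real safety difference harder to see.

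The trial is also open label at three sites. Section 6.1.2 relies on outcome collectors disregarding assignment. Definitions that staff must silently reinterpret weaken that safeguard and may be reinterpreted differently from site to site.

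**Working it through.** The protocol states no figure for these outcomes, so there is nothing to reproduce. The check applies each rule as written.

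**1. Cord gas (section 5.2.2, against the synopsis label).** Rule as written: pH < 7.0 or base excess (BE) > 12. Rule matching the label: pH < 7.0 or base deficit > 12, where base deficit = -BE, so BE < -12. No value can satisfy both BE > 12 and BE < -12, so the two base-excess limbs have no infant in common. The pairs below are assumed for illustration and do not come from the protocol.

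| pH | BE (mmol/L) | Event as written | Event with deficit > 12 |
|---|---|---|---|
| 6.95 | -16 | yes (pH limb) | yes |
| 7.05 | -14 | no | yes |
| 7.10 | -13 | no | yes |
| 7.25 | -4 | no | no |
| 7.45 | +13 | yes | no |

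The disagreements fall at pH 7.0 or more, where the base-excess limb alone decides. A minus sign lost in text extraction does not explain the wording. BE > -12 would also point the wrong way and would count every infant without a severe deficit.

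**2. Fever (section 5.2.2).** °C = (°F - 32)/1.8, so 38 °F = (38 - 32)/1.8 = 3.3 °C. In the other direction, 38 °C = 38 × 1.8 + 32 = 100.4 °F. Every woman exceeds 3.3 °C, so the number excludes no one. What remains of the definition is the word fever, the named diagnoses and the planned or started antibiotics. The unit is spelled out in full, so a misread symbol does not explain it.

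**3. Apgar (synopsis against section 5.2.2).** Scores 0, 1 and 2 are events under both <3 and ≤3. A score of 3 is an event only under ≤3. Scores of 4 and above are events under neither. The two differ at one score only.

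**The case against.** The strongest reply is that trained abstractors will not apply these definitions literally. A fever of 38 °F is impossible in a living patient and is plainly a unit slip. The synopsis label shows which direction of base excess was intended. The Data Collection Form built into REDCap (section 7.5) is not shown and may already hold the right rule. Sites may also record a base deficit rather than a signed base excess. All of this lowers the probability of miscounting. It does not make the text correct, because section 6.2 points abstractors to that text.

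Several stronger readings are tempting, and the protocol does not support them:

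- **That the acidemia outcome captures no acidosis.** The failure is confined to one limb of an either-or rule. The pH < 7.0 limb works for arterial and venous samples.
- **That the infection outcome reduces to any antibiotic use.** The numerical threshold is inert, but the word fever and the named diagnoses remain.
- **That the Apgar conflict is of equal weight.** Section 5.2.2 is where outcomes are defined and would normally govern over a synopsis list. The synopsis sign may also be an extraction artefact (≤ read as <), which cannot be settled from the text.
- **That the trial's safety assessment fails.** The neonatal composite in section 5.2.2 lists none of these three outcomes as a component. Death, intensive-care admission, haemorrhage and laceration outcomes are untouched. The monitoring board reviews adverse events at least quarterly (section 7.12).

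**Conclusion.** Two secondary safety outcomes are misdefined as written, and they should be corrected before analysis. The base-excess error is the more substantive. On signed values, its limb adds no infant with a deficit above 12 and can add infants with marked alkalosis. The Fahrenheit threshold is an evident unit error that makes the temperature condition inert if taken literally. The Apgar mismatch is minor.

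The conclusion about the text needs no assumption beyond the meaning of base excess and the temperature conversion. Any actual miscounting rests on three things the protocol does not show: that signed base excess is recorded, that the data form or derivation code copies the protocol wording, and that the wording is applied literally. No event rates are given for these outcomes, so the number of women or infants affected cannot be calculated. The primary outcome and the sample size of 988 do not depend on these definitions.

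**What to change.** In section 5.2.2, write base deficit > 12 mmol/L (base excess < -12 mmol/L) for both arterial and venous samples, and change the fever unit to Celsius. Align the Apgar cut in the synopsis with the one in section 5.2.2.

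Then check the REDCap fields, the abstraction instructions and any derivation code at all three sites against the corrected wording. Enrolment was expected to begin in October 2021 (section 5.1.1), so data already collected matter. Re-derive these outcomes for women already enrolled only if the check shows that the wrong rule was applied.

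The cost is three wording changes in an IRB amendment and one data-dictionary check. If re-derivation proves necessary, it is a recalculation where pH, base excess, temperature and Apgar were stored as values, and a return to the chart where only yes/no flags were kept. Making the correction before the groups are compared avoids a post hoc change to safety outcomes.
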